## 8.7 Pharmacokinetic Analysis

Intense PK sampling for APR-548 and the metabolites M8 and M10 will be performed in the safety run-in period on Days 1, 2, 4 and 5 of monotherapy, and on Cycle 1 of combination therapy on Days 1, 2, 4, 5. Sparse PK sampling for APR-548 and the metabolites M8 and M10

will be performed in every subsequent cycle on Day 1. Intense PK sampling for azacitidine will be performed in Cycle 1 on Days 1, 2, 4 and 5.

PK sampling for MQ-H2O, MQ-Cys and MQ-GSH will be implemented for individual subjects at selected centers. Samples will be collected in the safety run-in period on Days 4 and 5 of monotherapy and on Cycle 1 of combination therapy on Days 4 and 5.

Non-compartmental methods will be used to derive PK parameters for APR-548, the metabolites and azacitidine ( $C_{max}$ ,  $T_{max}$ ,  $T_{1/2}$ , AUC, CL/F and Vd/F). The PK of the study drugs and metabolites will be summarized using descriptive statistics (mean, standard deviation, CV% mean, geometric mean, CV% geometric mean). The concentration data for APR-548 will be evaluated using popPK analysis in combination with data from other studies.

During the dose escalation part of the safety run-in and Cycle 1 of the combination treatment, PK analysis of APR-548 and its metabolites will be conducted on an ongoing basis to allow review of the PK data prior to the dose escalation decision. Prediction of APR-548 for human PK will be updated on an ongoing basis to ensure that the exposure levels at the next dosing cohort do not exceed the pre-specified average maximum levels. Furthermore, PK variability will also be taken into account to ensure that the exposure levels in an individual will not exceed the pre-specified individual maximum levels. Exploratory exposure/safety analysis will be conducted on an ongoing basis for APR-548 and the metabolites to detect any relationship of safety signals with exposure levels and to guide the dose selection for the next cohort. If additional preclinical data indicate that more differentiated safety margins should be applied for one or more APR-548 metabolites, the protocol will be amended accordingly.

## **8.8 Exploratory analyses**

Descriptive statistics/results from exploratory analyses will be written. Results for PD biomarkers will include marker changes in different blood cell populations; results for response prediction and monitoring may include but are not limited to *TP53* VAF by NGS, mutations in other genes by NGS, RNA expression.

# **9.0 QUALITY CONTROL AND QUALITY ASSURANCE PROCEDURES**

## **9.1 Monitoring of the Study and Regulatory Compliance**

The project manager, or designee, will make an initiation site visit to each institution to review the protocol and its requirements with the investigator(s), inspect the drug storage area, fully inform the investigator of his/her responsibilities and the procedures for assuring adequate and correct documentation. During the initiation site visit the eCRFs will be reviewed. Other pertinent study materials will also be reviewed with the investigator's

research staff. During the course of the study, the monitor will make regular site visits in order to review protocol compliance, examine eCRFs and individual subject's medical records and assure that the study is being conducted according to pertinent regulatory requirements. All eCRF entries will be verified with source documentation. The review of medical records will be done in a manner to assure that subject confidentiality is maintained.

## **9.2 Curricula Vitae and Financial Disclosure of Investigators**

All Principal Investigators will be required to provide a current signed and dated curriculum vitae, a completed FDA Form 1572 and a financial disclosure statement to Sponsor's monitoring CRO. All Sub-Investigators will be required to provide a current curriculum vitae and a financial disclosure statement to Sponsor's monitoring CRO.

## **9.3 Protocol Modifications**

No modification of the protocol should be implemented without the prior written approval of the Sponsor or the Sponsor's representative. Any such changes which may affect a subject's treatment or informed consent, especially those increasing potential risks, must receive prior approval by the IRB/IEC. The exception to this is where modifications are necessary to eliminate an immediate hazard to trial subjects, or when the change involves only logistical or administrative aspects of the trial (e.g., change in monitor, change in telephone number). Other administrative revisions which may impact the clinical portion of a study will be duly reported to the IRB/IEC by the Principal Investigator.

## **9.4 Publication Policy**

The publication of the results of the study will be subject to the terms and conditions of the clinical trial agreement between the Sponsor and Investigators. Sponsor approval is required for publication of any data from this trial.

# **10.0 ETHICAL CONSIDERATIONS**

## **10.1 Informed Consent**

The investigator will obtain written informed consent from each subject, or their authorized representative, participating in the study. The form must be signed, witnessed, and dated. The informed consent form will contain all the Essential Elements of Informed Consent set forth in 21 CFR, Part 50, the European Union Directive 2001/20/EC and its associated Detailed Guidances, European Union GCP Directive 2005/28/EC, the ICH Guideline for GCP, Section 4.8, and the terms of the Declaration of Helsinki (2013). Copies of the signed document should be given to the subject and filed in the investigator's study file, as well as the subject's medical record if in conformance with the institution's Standard Operating Procedures.

## **10.2 Institutional Review Board/Independent Ethics Committee**

The study will not be initiated without approval of the appropriate IRB/IEC and compliance with all administrative requirements of the governing body of the institution. This protocol, consent procedures, and any amendments must be approved by the IRB/IEC in compliance with current regulations of the FDA and the European Union as applicable and in accordance with ICH/GCPs. A letter of approval will be sent to the Sponsor prior to initiation of the study and when any subsequent modifications are made. The IRB/IEC will be kept informed by the investigator, Sponsor's monitoring CRO or the Sponsor, as required by national regulations, as to the progress of the study as well as to any serious and unexpected AEs.

## **10.3 Subject Privacy**

In order to maintain subject confidentiality, all eCRFs, study reports and communications relating to the study will identify subjects by initials and assigned subject numbers; subjects should not be identified by name. In accordance with local, national or federal regulations, the investigator will allow the Sponsor or designee personnel access to all pertinent medical records in order to verify the data gathered on the eCRFs and to audit the data collection process. Regulatory agencies such as the US FDA may also request access to all study records, including source documentation for inspection. Clinical information will not be released without the written permission of the subject as outlined in the subject consent form.

# **11.0 DATA HANDLING AND RECORDKEEPING**

## **11.1 Data to be Entered Directly in the Case Report Form**

The eCRF will be the source record.

## **11.2 Recording of Data**

Data collected during the study will be entered in the subject's eCRF by the investigational site staff. The staff will keep records of the subject's visit in the files considered as source documents for the site, e.g., hospital chart, research chart. The investigator will be responsible for the recording of all data on the eCRF and for submitting the data to the Sponsor or their designee in a timely manner. Should any value be significantly different from normal, the investigator will comment in the appropriate sections provided in the eCRF.

The investigator will provide access to his/her original records to permit a representative from the Sponsor to verify the proper transcription of data.

### **11.3 Study Records**

U.S. Federal laws require that an investigator maintain all study records for the indication under investigation for two years following the date a Product Licensing Application is approved or, if no application is to be filed or if the application is not approved for such indication, until two years after the investigation is discontinued and the FDA is notified.

## APPENDIX I - Cockcroft-Gault Equation

Males:

$$\text{Creatinine CL} = \frac{\text{Weight (kg)} \times (140 - \text{Age})}{72 \times \text{serum creatinine (mg/dL)}}$$

Females:

$$\text{Creatinine CL} = \frac{\text{Weight (kg)} \times (140 - \text{Age})}{72 \times \text{serum creatinine (mg/dL)}} \times 0.85$$

## APPENDIX II - ECOG Performance Status

Grade	
0	Fully active, able to carry on all pre-disease performance without restriction.
1	Restricted in physically strenuous activity but ambulatory and able to carry out work of a light or sedentary nature, e.g., light housework, office work.
2	Ambulatory and capable of all self-care but unable to carry out any work activities. Up and about more than 50% of waking hours.
3	Capable of only limited self-care, confined to bed or chair more than 50% of waking hours.
4	Completely disabled. Cannot carry on any self-care. Totally confined to bed or chair.
5	Dead.

### APPENDIX III - Acceptable Contraceptive Methods

• Male or female condom with or without spermicide

• Cervical cap, diaphragm or sponge with spermicide

Effective Contraceptive Methods That Are User Dependent a
 
Failure rate of <1% per year when used consistently and correctly.
 

• Combined (estrogen- and progesterone-containing) hormonal contraception b

◦ Oral

◦ Intravaginal

◦ Transdermal

◦ Injectable

• Progestogen-only hormonal contraception b

◦ Oral

◦ Injectable

Effective Methods That Have Low User Dependency
 
Failure rate of <1% per year when used consistently and correctly.
 

• Progesterone-only contraceptive implant b, c

• Intrauterine hormone-releasing system (IUS) b

• Intrauterine device (IUD)

• Bilateral tubal occlusion

• Vasectomized partner
 
A vasectomized partner is an effective contraception method provided that the partner is the sole male sexual partner of the female of childbearing potential and the absence of sperm has been confirmed. If not, an additional effective method of contraception should be used.


• Sexual abstinence
 
Sexual abstinence is considered an effective method only if defined as refraining from heterosexual intercourse during the entire period of risk associated with the study treatment. The reliability of sexual abstinence needs to be evaluated in relation to the duration of the study and the preferred and usual lifestyle of the participant.)
 
Notes:
 
Use should be consistent with local regulations regarding the use of contraceptive methods for participants of clinical studies.
 
a) Typical use failure rates are lower than perfect-use failure rates (i.e., when used consistently and correctly).
 
b) If hormonal contraception efficacy is potentially decreased due to interaction with study treatment, condoms must be used in addition to the hormonal contraception during the treatment period and for at least 120 days, (corresponding to time needed to eliminate study treatment plus 30 days for study treatments with genotoxic potential) after the last dose of the study treatment.
 
c) If locally required, in accordance with Clinical Trial Facilitation Group (CTFG) guidelines, acceptable hormonal contraceptives are limited to those which inhibit ovulation.

**APPENDIX IV - New York Heart Association (NYHA) Classification**

NYHA Grading		MET*
Class I	No limitations. Ordinary physical activity does not cause undue fatigue, dyspnea or palpitations (asymptomatic LV dysfunction)	>7
Class II	Slight limitation of physical activity. Ordinary physical activity results in fatigue, palpitation, dyspnea or angina pectoris (mild Congestive Heart Failure (CHF)).	5
Class III	Marked limitation of physical activity. Less than ordinary physical activity leads to symptoms (moderate CHF)	2 – 3
Class IV	Unable to carry on any physical activity without discomfort. Symptoms of CHF present at rest (severe CHF).	1.6

\*MET (metabolic equivalent) is defined as the resting  $VO_2$  for a 40-year-old 70-kg man.

1 MET = 3.5 mL  $O_2$ /min/kg body weight.

**APPENDIX V - Response Criteria for Subjects with MDS and CMML According to IWG 2006 Criteria**

Altering Disease Natural History	
CR	Bone marrow: ≤5% myeloblasts with normal maturation of all cell lines Persistent dysplasia will be noted Peripheral blood: Hemoglobin ≥11 g/dL Platelets ≥100 × 10  /L Neutrophils ≥1.0 × 10  /L Blasts 0%
PR	All CR criteria if abnormal before treatment, except: Bone marrow blasts decreased by ≥50% over pretreatment but still >5% Cellularity and morphology not relevant
Marrow CR	Bone marrow: ≤5% myeloblasts and decrease by ≥50% over pretreatment Peripheral blood: if HI responses, they will be noted in addition to marrow CR
Stable disease (SD)	Failure to achieve at least PR, but no evidence of progression for >8 weeks
Failure	Death during treatment Disease progression characterized by worsening of cytopenia, increase in % of bone marrow blasts, or progression to a more advanced MDS FAB subtype than pretreatment
Disease Progression (PD)	For subjects with: Less than 5% blasts: ≥50% increase in blasts to >5% blasts 5-10% blasts: ≥50% increase in blasts to >10% blasts 10-20% blasts: ≥50% increase in blasts to >20% blasts 20-30% blasts: ≥50% increase in blasts to >30% blasts Any of the following: At least 50% decrement from maximum remission/response levels in granulocytes or platelets Reduction in hemoglobin (Hgb) concentration by ≥ 2 g/dL - Transfusion dependence
Cytogenetic Response	
Complete	Disappearance of the chromosomal abnormality without appearance of new ones
Partial	At least 50% reduction of the chromosomal abnormality
HI	
Erythroid response (HI-E) (Pretreatment <11 g/dL)	Hgb increase by ≥1.5 g/dL Relevant reduction of units of RBC transfusions by an absolute number of at least 4 RBC transfusions/8 weeks compared with the pretreatment transfusion number in the previous 8 weeks. Only

	RBC transfusions given for a Hgb of $\leq 9.0$ g/dL pretreatment will count in the RBC transfusion evaluation
Platelet response (HI-P) (Pretreatment $<100 \times 10^9$ /L)	Absolute increase of $\geq 30 \times 10^9$ /L for subjects starting with $>20 \times 10^9$ /L Increase from $<20 \times 10^9$ /L to $>20 \times 10^9$ /L and by at least 100%
Neutrophil response (HI-N) (Pretreatment $<1.0 \times 10^9$ /L)	At least 100% increase and an absolute increase of $>0.5 \times 10^9$ /L

### Progression/Relapse Criteria for Subjects with MDS/CMML

Altering Disease Natural History	
Disease Progression (PD)	
For subjects with:
 
Less than 5% blasts: <math>\geq 50\%</math> increase in blasts to <math>>5\%</math> blasts
 
5-10% blasts: <math>\geq 50\%</math> increase in blasts to <math>>10\%</math> blasts
 
10-20% blasts: <math>\geq 50\%</math> increase in blasts to <math>>20\%</math> blasts
 
20-30% blasts: <math>\geq 50\%</math> increase in blasts to <math>>30\%</math> blasts
 
Any of the following:
 
At least 50% decrement from maximum remission/response levels in granulocytes or platelets
 
Reduction in hemoglobin (Hgb) concentration by <math>\geq 2</math> g/dL
 
Transfusion dependence

Disease transformation	Transformation to AML (30% or more blasts)
Relapse after CR or PR	
At least one of the following:
 
Return to pretreatment bone marrow blast %
 
Decrement of <math>\geq 50\%</math> from maximum remission/response levels in granulocytes or platelets
 
- Reduction in Hgb concentration by <math>\geq 1.5</math> g/dL or transfusion dependence

HI	
Progression/relapse after HI	
At least one of the following:
 
At least 50% decrement from maximum response levels in granulocytes or platelets
 
Reduction in Hgb by <math>\geq 1.5</math> g/dL
 
Transfusion dependence

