Overall, *TP53*-mutant MDS and AML patients have a median OS ranging from 5-9 months with 8 months representing the best estimate when restricting to MDS and oligoblastic AML (20-30% blasts). Together, these data highlight the dismal outcomes of *TP53*-mutant MDS patients and the dire need for the development of novel therapeutic strategies, particularly in this patient population.

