## 2.10 Subject Population

This study will enroll adult male and female subjects of age  $\geq 18$  years with documented diagnosis of *TP53*-mutant MDS, according to the World Health Organization (WHO) classification (<20% blasts). Subjects with relapsed/refractory *TP53*-mutant MDS will be allowed in the study.

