### 3.2 Secondary Objectives

1. To assess preliminary clinical activity of APR-548 administered in combination with azacitidine.
  - a. Rate of CR
  - b. Duration of CR (DOCR)
  - c. ORR
  - d. Duration of ORR
  - e. Rate of and time to development of AML transformation, as defined by WHO criteria
  - f. OS
  - g. Relapse-free survival (RFS)
  - h. Rate of transition to hematopoietic stem cell transplant (HSCT)
  - i. Rate of red blood cell (RBC) and/or platelet transfusion independence (TI) for 8 weeks
2. To characterize PK of APR-548 after single and multiple dosing when given orally (p.o.)
3. To evaluate the PK drug-drug interaction between APR-548 and azacitidine.

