### 8.3.2 Secondary

1. Rate of CR
2. DOCR, defined as the time from documentation of CR to disease relapse
3. DOR, defined as the time from documentation of tumor response to disease relapse/progression or death as a result of any cause
4. ORR is the proportion of subjects achieving HI, PR, CR, marrow CR by modified IWG 2006 criteria
5. Rate of and time to AML transformation, according to WHO criteria
6. OS

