## WHO MDS

WHO Category	Peripheral blood	Bone marrow
MDS with single lineage dysplasia (MDS-SLD)	Cytopenia (1-2 lines) <1% blasts	Dysplasia (1 line) <5% blasts RS <15%/ † >5% †
MDS with ring sideroblasts (MDS-RS)*	Cytopenia (1-3 lines) <1% blasts	Dysplasia (1-3 lines) <5% blasts RS >15%/ † >5% †
MDS with multi-lineage dysplasia (MDS-MLD)	Cytopenia (1-3 lines) <1% blasts	Dysplasia (2-3 lines) <5% blasts RS <15%/ † >5% †
MDS with excess blasts type I & II (MDS-EB-1 & MDS-EB-2**)	Cytopenia (0-3 lines) Type I: 2-4% blasts Type II: 5-19% blasts	Dysplasia (1-3 lines) Type I 5-9% blasts Type II 10-19% blasts
MDS with isolated del(5q)***	Cytopenia (1-2 lines) <1% blasts	Dysplasia (1-3 lines) < 5% blasts
MDS unclassified (MDS-U)****	Cytopenia (0-3 lines) 1% or <1% blasts	Dysplasia (1-3 lines) <5% blasts

Cytopenias defined as: hemoglobin <10 g/dL; platelet count <100 × 10^9/L; and absolute neutrophil count <1.8 × 10^9/L.

To be classified as dysplasia, >10% of any cell lineage must be dysplastic. PB monocytes must be <1 × 10^9/L.

†If *SF3B1* mutation is present.

\* Subclassified as MDS-RS with single or multi-lineage dysplasia (MDS-RS-SLD or MDS-RS-MLD). Pancytopenia with RS is classified as MDS-RS-MLD.

\*\* Presence of Auer rods is classified as MDS-EB-2.

\*\*\* Del(5q) alone or with 1 additional abnormality except -7 or del(7q).

\*\*\*\* 1% peripheral blasts need to be confirmed on 2 separate occasions to make a diagnosis of MDS-U. MDS-U diagnosis is also made with SLD and pancytopenia or MDS defining cytogenetic abnormality in the absence of cytopenias.

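### AML transformation is a WHO-defined endpoint, but the response appendix prints a 30% blast cut-off; if that line is applied, no subject at 20-29% blasts counts as AML

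*Combined protocol and SAP*

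**What the plan says.** The endpoint is tied to WHO criteria wherever it is listed. Section 3.2 has "Rate of and time to development of AML transformation, as defined by WHO criteria" and Section 8.3.2 has "Rate of and time to AML transformation, according to WHO criteria"; the Synopsis agrees with both. None of these prints a blast percentage.

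The protocol's own text places the WHO boundary at 20%:
- Section 2.10 describes the population as MDS "according to the World Health Organization (WHO) classification (<20% blasts".
- In the WHO MDS table of Appendix VI, the highest marrow band is "Type II 10-19% blasts". The CMML table stops below 20% in both blood and marrow.
- The background in Section 2.2 speaks of "oligoblastic AML (20-30% blasts".

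Disease assessments follow Appendix V (Table 12, footnote l, and Section 6.7.1). Its progression and relapse table defines disease transformation as "Transformation to AML (30% or more blasts". Its progression rule for the band just under the WHO limit is "10-20% blasts: ≥50% increase in blasts to >20% blasts".

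Sections 7.2.3 and 8.6 run time to AML from the first treatment day to AML onset by Kaplan-Meier, and analyse the AML rate in the same way as the CR rate. They neither give a threshold nor say which appendix applies.

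**The concern.** One endpoint has two possible event definitions. The named one (WHO) starts AML at 20% blasts; the one printed in the table that sites hold at each assessment starts it at 30%. Appendix VI reprints WHO classes for MDS and CMML but has no AML row, so an assessor who looks for a transformation criterion finds the 30% line.

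At stake are the count and the date of every transformation in the 20-29% band. If some sites use WHO and others use Appendix V, the pooled rate mixes two endpoints. A missed event may also stay missed. After the End of Treatment visit, Section 6.9 requires further response assessment only for responders who stop for a reason other than relapse and for transplanted subjects. A subject who stops at 25% blasts may never have 30% documented.

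**Working it through.** **Inputs.** WHO limit for MDS: below 20% (Section 2.10, Appendix VI). Transformation line: 30% or more (Appendix V). Progression by blasts from a 10-20% baseline: a rise of at least 50%, to above 20% (Appendix V). Denominator: 6 × 6 + 10 = 46, which reproduces the stated maximum sample size. No AML rate, event count or power is stated for this endpoint.

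**1. AML count.** Take whole-percent baselines 0-19% (20 values) and follow-up values 20-29% (10 values), which gives 20 × 10 = 200 pairs. With AML at 20% or more, 200 of 200 are AML. With AML at 30% or more, 0 of 200 are.

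**2. Direction.** A subject who reaches 30% has already reached 20%. So the events under the 30% rule are a subset of those under the WHO rule, and each occurs on the same date or later. The rate can only fall and time to AML can only lengthen.

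**3. Does the progression rule catch these subjects?** With the rise measured from baseline b, progression by blasts needs a follow-up of at least 1.5b and above the band limit.
- Baseline below 10%: the highest whole-percent case is 1.5 × 9 = 13.5%, so every rise to 20-29% is progression.
- Baseline 10-13%: 1.5b is at most 19.5%, so only a follow-up of exactly 20% escapes.
- A gap strictly above 20% needs 1.5b > 20, that is b > 13.3% (about 13.4% upward).

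| Baseline | 1.5 × baseline | Follow-up values that are not progression by blasts | Pairs |
|---|---|---|---|
| 10-13% | 15-19.5% | 20 only | 4 |
| 14% | 21% | 20 | 1 |
| 15% | 22.5% | 20-22 | 3 |
| 16% | 24% | 20-23 | 4 |
| 17% | 25.5% | 20-25 | 6 |
| 18% | 27% | 20-26 | 7 |
| 19% | 28.5% | 20-28 | 9 |

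The total is 4 + 1 + 3 + 4 + 6 + 7 + 9 = 34 of 200 pairs, all from baselines of 10-19%. Leaving out follow-up of exactly 20%, it is 24 of the 90 pairs from those baselines. Baseline 10% is placed in the 10-20% band here, because the printed bands share their end points. Example: 18% to 25% is 25/18 − 1 = 38.9%, below 50%, so it is not progression by blasts, and it is below 30%. The pair counts describe the rules; they are not a forecast of how many subjects will be affected.

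**4. Size per subject.** One reclassified subject moves the AML rate by 1/46 = 2.2 points overall, 1/10 = 10 points if the ten additional RP2D subjects are summarised alone, and 1/6 = 16.7 points in a six-subject cohort. Section 8.0 presents data by dose level.

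**5. Illustration with assumed counts** (the documents give none). Suppose 14 of 46 subjects have AML by WHO, and some of them are recorded only at 20-29%:

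| Not counted | AML counted | Rate | Exact 95% CI |
|---|---|---|---|
| 0 | 14 | 30.4% | 17.7-45.8 |
| 2 | 12 | 26.1% | 14.3-41.1 |
| 4 | 10 | 21.7% | 10.9-36.4 |
| 6 | 8 | 17.4% | 7.8-31.4 |

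**6. Duration of response.** In Appendix V, relapse after CR or PR includes marrow blasts returning to the pretreatment level. Entry is below 20%, so a CR or PR subject whose marrow blasts reach 20% has passed that level and has relapsed. The list for loss of hematological improvement has no blast criterion, and the relapse row names only CR and PR. Any spill-over into DOR is therefore mainly in HI or marrow-CR responders.

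**The case against.** The strongest reply is that the endpoint is not undefined. WHO criteria are named in every list, the analysis text never points to Appendix V for AML, and Appendix V is headed as IWG 2006 response criteria. On that reading the 30% line is a leftover of a reprinted table and WHO governs. This is a fair reading, and a site that follows it introduces no bias. It does not remove the conflict: Appendix V is the working table at disease assessments, its transformation row says 30%, and no sentence says that the row is not used for the endpoint. The case report form is not among the documents. If it captures blast percentages, WHO AML could be derived later, but the plan does not say so.

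Three stronger readings are tempting, and the documents do not support them:
- **Sites have no indication of a 20% limit.** They do, in Sections 2.2, 2.4 and 2.10 and in Appendix VI. What is missing is an explicit WHO AML definition attached to the endpoint.
- **A subject going from 18% to 25% is neither AML nor progression.** This is shown only for the blast rule. A hemoglobin fall, a granulocyte or platelet decrement, or transfusion dependence also meets progression, and the Failure row mentions rising marrow blasts without a threshold.
- **Response results are broadly inflated.** Step 6 confines the DOR effect mainly to HI and marrow-CR responders. A subject at 20-29% cannot be CR, PR or marrow CR at that assessment, so best response is barely touched.

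**Conclusion.** The plan is wrong as written on this point: the stated endpoint and the printed transformation criterion disagree by ten percentage points of blasts, and nothing reconciles them. If the Appendix V line is applied, the AML rate can only be lower and time to AML longer than under the stated definition. It should not be inferred that the reported results will be biased, because that depends on which definition sites and programmers use. The total shift cannot be derived without a blast distribution or an AML rate; per subject it is 2.2 points at N = 46.

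The additional gap, in which a subject does not meet progression by blasts either, is limited to baselines of about 13.4% to below 20%, plus exactly 20% reached from 10-13%. It assumes that the rise is measured from the pretreatment value. AML is a descriptive secondary endpoint, so the DLT and RP2D conclusions do not depend on it.

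**What to change.** - In Sections 7.2.3 and 8.6, state one AML definition for the endpoint: WHO AML, 20% or more blasts in blood or marrow, consistent with Section 2.10 and Appendix VI.
- Date AML at the first assessment that meets the definition, whether or not progression is also met.
- Mark the 30% line in Appendix V as not used for this endpoint. If comparison with data on the older cut-off is wanted, tabulate the 30% count as a secondary result.
- Leave the progression rows, including the 20-30% band, for the sponsor to reconcile. Progression is a treatment-discontinuation criterion (Section 4.10.1), so changing those rows reaches beyond this endpoint.

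Cost: a sentence in each of the two sections, a note in Appendix V, and a check that the case report form records what is needed. No extra tests are required. The downside for the sponsor is that the reported AML rate may be higher and time to AML shorter.
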